4.4.2.4. Delivery Device

The TDS-IM V1.0 and TDS-ID devices are investigational. To date, the TDS-IM V1.0 device has been used as the means of administration in a total of 25 completed and ongoing clinical studies of DNA based vaccine candidates, with > 1000 subjects enrolled. These studies have been conducted in the United States, United Kingdom, European Union, Korea, and in East Africa. To date, a total of over 700 subjects have been dosed using the TDS-IM V1.0 device in these studies (including subjects receiving either the test DNA or placebo). Subjects have been administered regimens of up to 5 administrations at DNA doses of up to 8.0 mg per time point. In one study, allowing continuing dosing, subjects have received up to an additional 10 administrations delivered on a quarterly schedule. Doses have been administered in the medial deltoid and/or the quadriceps muscles either as a single injection in one muscle site (approximately half of subjects to date) or as 2 injections in 2 separate muscle sites (approximately half of subjects to date).

To date, the TDS-ID device has been used as the means of DNA vaccine administration in one completed and 2 ongoing clinical studies sponsored by Ichor. In the completed study, 20 subjects received the TDS-ID administration procedure either for delivery of a VEEV DNA vaccine candidate or placebo control. In the vaccine arm of the study, subjects received sequences of up to 3 administrations at DNA doses of either 0.08 mg or 0.3 mg per time point. Doses were administered in the skin in the deltoid region. Adverse reactions associated with the use of the device include acute pain at the time of electroporation application in almost all subjects. Mild, transient bleeding at the sites of electrode penetration was commonly observed following removal of the device. These included injection site pain, erythema, induration, swelling,

tenderness, bruising, punctures at the site of needle penetration, eschar formation at the site of needle penetration, and/or localized pigmentation changes. The associated injection site reactions typically resolved within 24-72 hours following administration.

4.5. Known and Potential Risks and Benefits to Human Subjects

4.5.1. Risks/Discomfort to Subjects and Precautions to Minimize Risk

The following safety profile is based on the aforementioned clinical studies with HTNV DNA and PUUV DNA vaccines, plus a VEEV DNA vaccine trial led by Ichor, and includes a brief description of possible procedures to ameliorate risks and symptoms. The potential risks of this trial are those associated with having blood drawn, use of the TDS-IM V1.0 and TDS-ID to deliver the study products, and possible reactions to the experimental vaccines. The TDS-IM V1.0 device also carries a theoretical risk that excessive energy could be delivered to the local tissues of the volunteer. There may be potential risk related to breach of confidentiality, as well as other unknown risks, discomforts, or side effects. All known risks and precautions described are explained in detail in the informed consent. In addition, it is important to note that this protocol investigates a combination product consisting of the DNA and the administration device, and that risks of local and systemic reactions for the 2 may necessarily need to be considered as a single phenomenon, and could be hard to attribute to either product or device.

4.5.1.1. Local Reactions

Local reactions in previous studies have included pain, stinging, itching, bruising, tingling, numbness and redness at the injection site (deltoid muscle or associated skin in that area of the arm), and sometimes affecting the arm distal to the site. Information about local reactions are described below for each device type.

TDS-IM V1.0 Device:

Adverse reactions associated with the use of the TDS-IM V1.0 device for DNA vaccine delivery and reported in almost all subjects include acute pain with localized muscle contractions during the application of the electrical fields. In the TDS-IM V1.0 study of the hantavirus DNA vaccines, brief, but intense, muscle contractions and associated local pain/discomfort during the period of EP administration were observed in essentially all subjects. Additional AEs associated with the administration procedure included minor, transient cutaneous bleeding at the sites of electrode and injection needle penetration, and mild to moderate injection site soreness/bruising typically lasting for 24 to 72 hours, but in a small number of cases, up to 7 days post administration. Occasionally, subjects have also reported mild, transient paresthesia (tingling) or hypoesthesia (numbness) in the injected limb or fingers for a few seconds or minutes following electric field application. Over the 24-72 hours after administration, administration site soreness, erythema, induration and/or eschar formation of mild to moderate severity are commonly reported. Other injection site findings of mild severity including bruising and/or hematoma have been reported occasionally. The associated injection site reactions have typically been of mild to moderate severity and typically resolve within 24-72 hours following administration. However, in rare instances, subjects have reported severe local site soreness which resolved by 48 hours post administration.

There has been at least one reported instance of an aborted TDS-IM V1.0 administration procedure with observations consistent with injection needle contact with the underlying bone. This was associated with acute pain at the penetration site and increased difficulty in the withdrawal of the device. Subsequent inspection of the Cartridge revealed deformation of the needle consistent with impact on the bone. The TDS-IM V1.0 device registered an error code and no vaccine was delivered. This was believed to be due to an inaccurate measurement of skinfold thickness. Following the incident, associated adverse events were limited to mild transient soreness at the penetration site. Although the specific cause of this event could not be definitively established based on the available information, inspection of the device was sufficient to rule out device malfunction (ie, the needle did not penetrate beyond the specified depth setting). To ensure intramuscular injection, proper selection of the injection site as well as assessment and setting of the injection depth are important factors in procedure administration. In particular, care should be taken in specific subjects or subject populations with low muscle mass (eg, sarcopenia) to ensure that an administration site with adequate muscle thickness (eg, vastus lateralis) is selected for injection. Specifically, any selected administration site should have sufficient muscle mass to accommodate the 1-inch/25-mm maximum penetration depth of the device. To mitigate the risk of this happening again, only the PI or qualified, designated personnel with PI oversight will take all skinfold measurements and study staff training on skinfold measurement and device usage will be performed and documented by Ichor for implementation of this study. This should decrease the possibility of inter-rater variability errors in measurement and avoid overestimations of soft tissue girth. The measurement may be repeated, as needed, throughout the study or if any study team member has a concern about the accuracy of the measurement (eg, if there seems to be a discrepancy between the volunteer's body habitus and the indicated depth setting for the TDS-IM V1.0 device).

There have been no occurrences of excessive energy delivery in any of the nonclinical and clinical studies conducted with the pulse stimulator to date.

TDS-ID Device:

To date, the TDS-ID device has been used as the means of DNA vaccine administration in one completed and 2 ongoing clinical studies sponsored by Ichor. The results of the VEEV DNA vaccine study have been published (Hannaman et al, 2016). Adverse reactions associated with the use of the TDS-ID device include acute pain at the time of electroporation application in almost all subjects. Mild, transient bleeding at the sites of electrode penetration was commonly observed following removal of the device. These included injection site pain, erythema, induration, swelling, tenderness, bruising, punctures at the site of needle penetration, eschar formation at the site of needle penetration, and/or localized pigmentation changes. The associated injection site reactions typically resolved within 24-72 hours following administration.

Consistent with the clinical safety experience from the VEEV DNA vaccine study, interim safety reports from the 2 ongoing clinical studies utilizing the TDS-ID device (clinicaltrials.gov # NCT02589795 and EUDRA CT# 2014-001997-33) have included mild to moderate injection site reactions including minor bruising and hematoma at the sites of administration.

No serious adverse events attributed to the device or administration procedure have been observed to date during any of the clinical studies utilizing the TDS-ID device.

Tolerability of TDS-IM V1.0 compared to TDS-ID device:

In the VEEV DNA vaccine study, which compared IM and ID-EP delivery, the results of a subject questionnaire revealed that the IM- and ID-EP procedures were both considered to be generally acceptable for prophylactic vaccine administration, with the acute tolerability of ID EP delivery judged to be greater than that of IM-EP delivery published ([Hannaman et al, 2016](#)).

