6. TRIAL DESIGN

6.1. Study Endpoints

Primary endpoints, correlating to the primary objective of the study, will include determining the nature, frequency, and severity of AEs and/or SAEs associated with TDS-EP-based administration of HTNV, PUUV and HTNV/PUUV DNA vaccines.

- The occurrence of solicited local and systemic AEs occurring from the time of each injection through 14 days following the procedure
- The occurrence of vaccine-related unsolicited AEs from the time of the first injection through 28 days following each injection
- The occurrence of SAEs from the time of the first injection through the final study visit (approximately 6 months post-last vaccination)
- The occurrence of clinical safety laboratory AEs through 14 days following each study vaccination

Secondary endpoints, correlating to the secondary objectives of the study will be to determine the proportion of seropositive subjects ($\text{PsVNA50} \geq 1:20$) and the final overall rate of seroconversion over all scheduled time points to study completion for each study group. GMT will be calculated using PsVNA50 .

- Determination of the proportion of seropositive subjects (defined as $\text{PsVNA50} \geq 1:20$) at each scheduled time point (eg, Days 0, 28, 56, 84 and 140)
- Determination of the final overall rate of seroconversion over all scheduled time points to study completion for each study group. Seroconversion is defined as a post-vaccination HTNV- or PUUV-specific titer of $\geq 1:40$, or a minimum four-fold rise compared to baseline titer, and all study volunteers will begin the study with a baseline titer < 20 (ie, seronegative).
- Determination of GMT of the PsVNA50 for HTNV- and PUUV-specific neutralizing antibodies at each scheduled time point for each study group and over all time points for each study group.

Exploratory endpoints, evaluated as part of the immunogenicity objectives, including calculation of PsVNA80 titers for HTNV and PUUV may be calculated from the collected data for informational purposes, and neutralization assays using other hantavirus PsV (eg, Seoul virus, Dobrava virus) may also be performed to evaluate levels of cross-neutralizing antibodies.

- Determination of GMT of neutralizing of the PsVNA80 for HTNV- and PUUV-specific neutralizing antibodies at each scheduled time point for which blood samples are taken for each study group and over all time points for each study group

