10.3.2. Solicited Adverse Event

A solicited AE is a predetermined event, identified in the Investigator's Brochure, which may reflect safety concerns related to the investigational product. The solicited AEs for this study include:

- Redness, swelling, bruising, pain, or tenderness at the injection site
- Fever
- Myalgia (general muscle aches)
- Headache
- Lymphadenopathy
- Axillary pain or discomfort
- Tachypnea
- Fatigue

Adverse events that are considered related to the TDS-ID and TDS-IM V1.0 devices include eschar formation, bleeding, tingling or numbness at injection site or hand/arm distal to site, and/or pigmentation changes. If any of these should occur, they will be captured as unsolicited adverse events.

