TABLE 3.1: Proportion of Seropositive Subjects at Each Blood Collection Time Point

Collection Point	Group 1 (N=X)		Group 2 (N=X)		Group 3 (N=X)		Group 4 (N=X)		Group 5 (N=X)		Group 6 (N=X)	
	n	%	n	%	n	%	n	%	n	%	n	%
1	x	xx										
	[x,x]		[x,x]		[x,x]		[x,x]		[x,x]		[x,x]	
2												
3												
4												
5												
6												
7												

Note: 95% confidence intervals for sample proportion in brackets

TABLE 3.2: Proportion of Subjects that Ever Seroconverted at Each Blood Collection Time Point

Collection Point	Group 1 (N=X)		Group 2 (N=X)		Group 3 (N=X)		Group 4 (N=X)		Group 5 (N=X)		Group 6 (N=X)	
	n	%	n	%	n	%	n	%	n	%	n	%
1	x	xx										
	[x,x]		[x,x]		[x,x]		[x,x]		[x,x]		[x,x]	
2												
3												
4												
5												
6												
7												

Note: 95% confidence intervals for sample proportion in brackets

TABLE 3.3: Duration of Seropositivity if Ever Seroconverted

	Group 1 (n=x)	Group 2 (n=x)	Group 3 (n=x)	Group 4 (n=x)	Group 5 (n=x)	Group 6 (n=x)
Mean						
Standard Deviation						
95% CI for Mean						
1st Quartile						
Median						
3rd Quartile						
Min						
Max						

TABLE 3.4: Geometric Mean Titers of the PsVNA50 at Each Blood Collection Time Point

Collection Point	Group 1 (N=X)		Group 2 (N=X)		Group 3 (N=X)		Group 4 (N=X)		Group 5 (N=X)		Group 6 (N=X)	
	μ	SD										
1	x	x	x	x	x	x	x	x	x	x	x	x
	[x,x]		[x,x]		[x,x]		[x,x]		[x,x]		[x,x]	
2												
3												
4												
5												
6												
7												

Note:

- μ = mean; SD = standard deviation
- 95% confidence intervals for sample proportion in brackets

TABLE 4.1: Safety Analysis Group Comparison: Ever Experienced Solicited Adverse Events

Group:	1	2	3	4	5	6	P-value ¹
N=	x	x	x	x	x	x	
% Reporting	xx	xx	xx	xx	xx	xx	
(95% CI)	(x,x)	(x,x)	(x,x)	(x,x)	(x,x)	(x,x)	
Pair 1	•	•					x
Pair 2		•	•				x
Pair 3				•	•		x
Pair 4	•				•		x
Pair 5		•			•		x
Pair 6		•				•	x
Pair 7			•		•		x

¹P-value obtained from a two-sided Fisher's exact test

TABLE 4.2: Safety Analysis Group Comparison: Ever Experienced Unsolicited Adverse Events

Group:	1	2	3	4	5	6	P-value ¹
N=	x	x	x	x	x	x	
% Reporting (95% CI)	xx (x,x)	xx (x,x)	xx (x,x)	xx (x,x)	xx (x,x)	xx (x,x)	x
Pair 1	•	•					x
Pair 2		•	•				x
Pair 3				•	•		x
Pair 4	•			•			x
Pair 5		•		•			x
Pair 6	•				•		x
Pair 7			•		•		x

¹P-value obtained from a two-sided Fisher's exact test

TABLE 4.3: Immunogenicity Analysis: Ever Seroconverted

Group:	1	2	3	4	5	6	P-value ¹
N=	x	x	x	x	x	x	

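### Four foreseen device reactions are recorded as unsolicited AEs, and the SAP's ever/never group test (Table 4.2) cannot separate them from other events

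*Protocol*

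**What the plan says.** **Classification.** Protocol 10.3.2 lists the solicited local reactions as "Redness, swelling, bruising, pain, or tenderness at the injection site". It then says that adverse events considered related to the two TDS "devices include eschar formation, bleeding, tingling or numbness at injection site or hand/arm distal to site, and/or pigmentation changes", and adds: "If any of these should occur, they will be captured as unsolicited adverse events".

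**Stated frequency (Protocol 4.5.1.1).**
- IM device: "administration site soreness, erythema, induration and/or eschar formation of mild to moderate severity are commonly reported". Soreness, erythema and induration correspond to solicited terms, so only eschar in that list belongs to the four. Bleeding is mentioned for IM without being called common. On tingling: "Occasionally, subjects have also reported mild, transient paresthesia (tingling) or hypoesthesia (numbness) in the injected limb or fingers".
- ID device: "Mild, transient bleeding at the sites of electrode penetration was commonly observed following removal of the device". Eschar and pigmentation change are listed without a frequency of their own.

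**Endpoint.** Protocol 6.1 and SAP 3.3 make this a primary endpoint: "The occurrence of vaccine-related unsolicited AEs from the time of the first injection through 28 days following each injection".

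**Group test.** SAP Appendix I contains "TABLE 4.2: Safety Analysis Group Comparison: Ever Experienced Unsolicited Adverse Events", a percentage of subjects per group with pairwise two-sided Fisher p-values. Its shell has no split by relatedness or device. Its first pair is Group 1 v Group 2, the same vaccine by ID and by IM. SAP 6.7 plans no multiplicity adjustment, and SAP 5 says that the group sizes were not chosen for power.

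**The concern.** A subject counts once in Table 4.2 whether the event is a trace of electrode bleeding or something nobody foresaw. If many subjects have a mark from at least one of three doses, most subjects in every group are already positive. Two things can then happen.

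- **Same route, different vaccine.** Marks raise both groups towards 100%, and a real difference in other unsolicited events shrinks.
- **Same vaccine, different route.** If the two devices leave marks at different rates, the p-value may reflect those marks while the table labels the result unsolicited AEs.

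There is also a wording gap. The endpoint says vaccine-related, but these four reactions are attributed to the devices. The plan should say that they count.

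**Working it through.** **Inputs from the documents.** 12 subjects in each of Groups 1 to 5 and 22 in Group 6 (Protocol 6.3.1); three doses; two-sided Fisher test (SAP Table 4.2); alpha 0.05 (Protocol 11.3). The plan gives no rate or power for this test, so there is no planned figure to reproduce.

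**The only AE counts that bear on the question** come from the earlier IM hantavirus study (Protocol 4.4.2.1.2). Its percentages reproduce:
- 76/246 = 30.9% of AEs were injection-site pain.
- 96/246 = 39.0% were related.
- 87/96 = 90.6% of the related AEs were pain, bruising or erythema, all solicited terms here.

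That leaves 96 − 87 = 9 related AEs that could be any of the four reactions. The five commonest terms make up 30.9 + 5.7 + 3.7 + 3.3 + 3.3 = 46.9% of AEs, leaving about 246 × 0.531 = 131. So related device marks were at most about 9/131 = 7% of the remainder. Within the related-only pool the share is indeterminate: anywhere from none to all of the 9. The study was IM only and may not have recorded minor marks as AEs. No comparable ID counts are given.

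**Illustration. All rates below are assumptions.** Let p be the chance of a mark at one dose, equal in both groups, and r the chance of any other unsolicited AE, independent of marks.
- Chance of a mark over three doses: q = 1 − (1 − p)³ if doses are independent; q = p if marks are fully correlated within subject.
- Observed rate: 1 − (1 − r)(1 − q), with r = 10% v 60%.
- Example, p = 0.10, independent: q = 1 − 0.9³ = 0.271. The rates become 1 − 0.9 × 0.729 = 34% and 1 − 0.4 × 0.729 = 71%, so a 50-point difference becomes 36 points.

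Fisher power by full enumeration:

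| Mark rate per dose | Dependence | q | Observed rates | Power, 12 v 12 | Power, 12 v 22 |
|---|---|---|---|---|---|
| 0 | – | 0 | 10% v 60% | 64% | 78% |
| 10% | independent | 0.27 | 34% v 71% | 32% | 47% |
| 10% | fully correlated | 0.10 | 19% v 64% | 50% | 65% |
| 30% | independent | 0.66 | 69% v 86% | 7% | 17% |
| 30% | fully correlated | 0.30 | 37% v 72% | 29% | 44% |

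**Route comparison.** Suppose only the marks differ (20% v 60% per dose) and other events are 20% in both groups.
- Independent doses: q = 1 − 0.8³ = 0.488 and 1 − 0.4³ = 0.936. Table 4.2 shows 1 − 0.8 × 0.512 = 59% v 1 − 0.8 × 0.064 = 95%, significant at 12 v 12 in 38% of trials.
- Fully correlated: 1 − 0.8 × 0.8 = 36% v 1 − 0.8 × 0.4 = 68%, significant in 24%.

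**The case against.** **The unsolicited category will consist mostly of procedure marks.** A reader might infer this, but no rate supports it. Only eschar with IM and bleeding with ID are called common, and the one earlier data set points the other way for IM. The objection stands.

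**Unforeseen events will be hidden.** Another tempting inference, and also unsupported. Protocol 11.1.1 and SAP 8 plan AE summaries by body system and preferred term for each group. Protocol 11.1.1 and SAP 8.5 plan a complete listing by subject. Unexpected AEs have Tables 2.3.3 and 2.3.4 and Listing 1.11.2. What remains is narrower: the pooling affects Table 4.2 and the totals in Table 2.2, and no SAP shell shows the device reactions by type, dose and device.

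**Table 4.2 is not the only group test.** Correct for the plan as a whole: Protocol 11.1.1 also applies Fisher's exact test to AEs by body system. Table 4.2 is the only one specific to unsolicited AEs.

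**Device reactions might drop out of every primary AE endpoint unless serious.** The narrow reading of vaccine-related allows this, but the text around it does not favour it. The lead-in to the primary endpoints in Protocol 6.1 covers AEs associated with TDS-EP administration, Protocol 4.3 defines the product as vaccine plus device, and 10.4 judges relatedness to that product. A clarification is enough.

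**A route difference in marks is a genuine safety finding.** True, since the primary objective covers both routes. The difficulty is that the pooled line cannot say what produced the difference.

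**The power loss depends on the contrast chosen.** Also true. At 10% v 30%, power at 12 v 12 is only about 10% with no marks at all, so there is little to lose. The plan disclaims power in any case.

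**Conclusion.** The concern holds in limited form. Reactions that the protocol foresees, two of them described as common on one device each, go into the unsolicited category. The only group test specific to that category is an ever/never binary that cannot tell them from other events. It can saturate when vaccines given by the same route are compared, and it can reflect electrode marks when routes are compared.

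The size is unknown. In the illustration, power falls from 64% to between 32% and 50% at a 10% mark rate per dose, and to between 7% and 29% at 30%, depending on how marks cluster within subjects. These figures rest on assumed mark rates, equal in both groups and independent of other events, and on a 10% v 60% contrast. What is at stake is the interpretation of an exploratory, unadjusted p-value and the clarity of the device-safety summary. The documents do not support saying that the endpoint will consist mainly of procedure marks or that unforeseen events will go unseen.

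**What to change.** Leave data collection and the overall unsolicited-AE counts as they are, so that the 36 subjects reported in Protocol Appendix B as already enrolled stay comparable with later ones. Then:

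1. In the SAP, before database lock, list the preferred terms for the four reactions named in Protocol 10.3.2 and flag them as device/procedure reactions.
2. Add one table of these reactions by event, dose, device and group, and maximum grade.
3. Present Table 4.2, and the unsolicited rows of Table 2.2, both with and without the flagged terms.
4. Keep any device reaction that is unexpected by severity in Tables 2.3.3 and 2.3.4. Removing the four events from those tables or from the headline counts would go too far, because an unusually severe eschar, for example, could then be lost.
5. In Protocol 6.1 and SAP 3.3, state that vaccine-related in this endpoint means related to the investigational product, vaccine or device, in line with Protocol 4.3 and 10.4.

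The cost is one extra table, one extra run of Table 4.2, and a short wording change. The protocol part needs the approvals in Protocol 14.1.2 and can wait for the next amendment. No new data are needed.
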